- 1. To determine the incidence of airway complications in patients undergoing general anaesthesia during the COVID-19 pandemic.
- 2. To identify components of the aerosol precaution bundle (including PPE and anaesthetic techniques) which may be associated with a greater risk of airway complications.

6 Study design & Flowchart

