6.1 Study Design

AeroComp is service evaluation exploring the incidence of airway complications amongst patients undergoing general anaesthesia for surgical procedures within NHS Trusts. All adult patients undergoing any surgical procedure (with the exception of obstetric procedures) with the primary method of anaesthesia planned to be general anaesthesia will be eligible for enrolment to this study. The study duration will encompass 5 days (patients being enrolled over a 96 hour consecutive window with a further day of follow-up data collection) with an estimated total of 3600 patients being included. Individual sites are free to choose their own data collection window between 1st November

2021 and 3rd December 2021 as long as the 96 hour window commences at 07:30 on a Monday and closes at 07:29 on a Friday.

Primary outcome:

 Incidence of airway complications at both induction and emergence, defined as a composite of: airway trauma, aspiration, dental/lip/mucosal injury, change of intubation device, desaturation, three or more laryngoscopy attempts, grade 3 or 4 laryngoscopy, difficult face mask ventilation, difficult supraglottic airway device (SAD) usage, emergency front-of-neck airway, failed tracheal intubation, laryngospasm, oesophageal intubation (immediate or delayed recognition), requirement of reintubation immediately after extubation, and need for second intubator.

Secondary outcomes:

- Risk of composite outcome of airway complications will be reported for each individual component of the aerosol precaution bundle.
- Individual complications that comprise the primary outcome.
- Subjective operator assessment of airway difficulty
- Unanticipated airway difficulties necessitating significant deviation from the original airway plan.
- Composite risk of airway complication and association with confirmed/suspected COVID-19 infection, known negative COVID-19 infection without any potential COVID-19 risks, and all other patients.

7 List selection

Operating lists from all participating NHS hospitals will be included, with patients from those lists being eligible. Both elective and emergency cases will be included. The centres and local investigators will be identified by the Pan-London Perioperative Audit and Research Network (PLAN) or other national trainee research networks.

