9.1 Data to be collected

Data will be collected on all operating lists with patients who meet inclusion criteria in participating hospitals. Each hospital taking part will have nominated staff who will be responsible for data collection.

For each day of the study the local investigating team will determine the total number of patients eligible for inclusion.

For each included patient, the anaesthetist or anaesthetic assistant (e.g. operating department practitioner, anaesthetic nurse) will be asked to complete a paper case record form (CRF; *Appendix* 2). Where more than one anaesthetist is involved, the most senior anaesthetist should be asked to complete the CRF.

Completed CRFs will be collected from the treating anaesthetic team. Local investigators will be responsible for ensuring accuracy and completeness of data. Where appropriate, this should include cross-checking with patient notes and other sources of information.

Completed CRFs will be stored in a secure location accessible by the local PI and other named members of the study team in accordance with NHS Information Governance standards. Information from each paper CRF, as well as the total number of eligible patients for each day of the project, will be entered via a secure web-based portal onto a secure database. The database will have data validation rules built-in to ensure accurate data entry (e.g. range checks, and field validation).

No patient-identifiable information will be uploaded to the secure database. Each site may elect to use a local ID upon the CRF to facilitate retrospective data capture within the immediate time frame of the project however this should be detached once the CRF is completed and will not form part of the dataset uploaded to the data capture server. Paper CRFs will be retained by the local study team in a locked, secure location in the hospital for a period of 6 months after the project ends to allow queries about study quality to be addressed during data cleaning and analysis. The local ID will not remain upon the CRF during this period.

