 - Airway devices utilised: facemask, supraglottic airway device; tracheal tube; other (including rigid bronchoscope, jet ventilator and transnasal humidified rapid-insufflation ventilatory exchange)
 - Airway techniques including: direct laryngoscopy; videolaryngoscopy; use of a flexible bronchoscope over which a tracheal tube is passed, categorised into whether performed awake or asleep
 - Use of cricoid force?

- Adjunct equipment including: bougie; stylet; Oxford or HELP pillow; high and lowflow nasal cannulae; aerosol boxes or drapes; as well as a free text option for other potential equipment

- Patient COVID-19 status:
 - Positive: RT-PCR or lateral flow test positive for SARS-CoV-2; OR symptoms consistent with COVID-19 with no SARS-CoV-2 test available; OR recent exposure to SARS-CoV-2
 - Negative: RT-PCR or lateral flow test negative for SARS-CoV-2 infection; AND actively cohorted with other COVID-19 negative patients for the entirety of their hospital stay prior to this operation; AND self-isolated according to institutional guidelines.
 - Unclear: No SARS-CoV-2 result available with no risk factors; OR not self-isolated according to institutional guidelines; OR not in a COVID-19-free pathway.
- Whether anaesthesia was terminated at the end of the procedure with a plan to wake up the patient (emergence from anaesthesia).

Airway complications:

- Number of tracheal intubation attempts.
 An attempt is defined by the number of times the laryngoscopy device is inserted or reinserted into the patient's airway.
- Best grade of laryngoscopy: modified Cormack and Lehane grading [9] into 1, 2a, 2b, 3 and 4.
- The following complications categorised into induction and emergence (defined as the period around the time of cessation of anaesthesia until hand over of patient to recovery/intensive care staff):
 - Airway trauma: evidence of airway bleeding or oedema.
 - Dental injury (arising solely from anaesthetic, rather than surgical, interventions)
 - Lip and mucosal injuries (arising solely from anaesthetic, rather than surgical, interventions)
 - Pulmonary aspiration: inhalation of oropharyngeal or gastric contents into the larynx and lower respiratory tract [10]
 - Change of intubation device: use of an additional airway device, e.g. change from supraglottic airway to tracheal tube, change from direct to videolaryngoscopy (or vice versa), use of bougie if not initially anticipated, change in type of laryngoscope e.g. McCoy vs Macintosh blade

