Shaw *et al.* [12] reported an incidence of 91 airway complications in 1874 patients (~5%). Therefore, assuming an anticipated 5% incidence of our primary outcome in our study population, a desired error of +/-1% (absolute error) of our estimate for the incidence, and a 95% confidence level of achieving the desired estimate precision, we calculate the sample size required for our study to be \geq 1822 patients (Appendix 4; [13]). For a conservative estimate, with 50 centres each performing 18 procedures a day, we expect 3600 patients to be included, allowing acceptable rates of detection of rare events.

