15.2 Appendix 2 – Sample Case Record Form (CRF)

AER	COMP	Study Day ¹ : D Monda	, ,	Study ID: Hospital	:	
PATIENT DETAILS		PATIENT COVID-19 STATUS		SURGICAL DETAILS		
Age: 18 to 60 to Sex: Male Fema Other	79 🗖 80 and over	 Positive (PCR/LFT positive; CC Negative (PCR/LFT negative a COVID-19 free pathway) 	WID-19 symptoms; recent exposure) nd self-isolated and cohorted in	Surgical urgency ² :	Severity ³ : D Mind D Inter D Majo	rmediate
ASA Score:	− 29.9 □ 30.0 − 34.9	Unclear (No test result availal isolated; not cohorted in COVID-		Specialty: Breast ENT Bariatric General Cardiac Gynaecology Cardiology Max-Fax Dental Neurosurgery Other:	 Ophthalmology Ortho/Trauma Plastics Radiology Thoracic 	TransplantUrologyVascular
ANAESTHETIC DETA				Procedure performed within main operating theat	re complex: D Yes	No
Start time ^{1,4} : Grade of initial airway manager ⁵ : PPE worn by anaest Eye protection:	 00:00 to 07:29 07:30 tilde CT1-2 ST5-7 Consultion CT/ST3-4 SAS/SCF Other Other 07:30 tilde 07:30 ti	Itant Grade of second her airway manager ^{5,6} :	5 B	AIRWAY COMPLICATIONS (tick all that apply) Tracheal intubation attempts ⁸ : 1 2 Best grade of laryngoscopy ⁸ : 1 2 Was the patient woken up at the end of surgery? ⁹	□ 3 □ >3 □ 2b □ 3 □ Yes □ No	□ 4
Respiratory	 Other Surgical face mask 		Hazmat suitOther	Airway complications: (tick all that apply)	Induction	Emergence ⁹
rotection:	 Disposable FFP2/3 respirator Re-usable FFP2/3 respirator Powered air purifying respira Other 		 Single pair of gloves Double pair of gloves Other 	Airway trauma Aspiration Change of intubation device Death ¹⁰		
IRWAY MANAGEN Induction:	MENT (tick all that apply) Inhalational Intravenous: non-RSI	Equipment:	Bougie Stylet Cofeed pillour	Dental injury Desaturation (SpO₂ ≤90%) Desaturation (SpO₂ ≤80%) Difficult mask ventilation (2-person technique)		
Dxygenation:	 Intravenous: RSI/modified RS Pre-oxygenation Post-induction mask ventilati Apnoeic oxygenation 	ion	 Oxford pillow High-flow nasal cannulae Low-flow nasal cannulae Clear plastic 'aerosol' box Other 	Difficult SAD (excessive leak, poor ventilation, hypo Emergency front-of-neck airway Failed tracheal intubation – continue with SAD		
Airway device:	 Face mask (as sole airway de Supraglottic airway device Tracheal tube Other⁷ 	Airway technique: Direct laryngoscopy Video laryngoscopy Flexible bronchosco		Failed tracheal intubation – awaken patient Laryngospasm not reversed with positive pressure Lip/mucosal injury	D	

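### Section 9.1 says aerosol boxes or drapes will be recorded, but the CRF prompts only for the box, so this barrier exposure is likely to be under-ascertained

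*Protocol*

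**What the plan says.** Two parts of the Protocol depend on exposure to each aerosol precaution. The second aim in section 5 is "To identify components of the aerosol precaution bundle (including PPE and anaesthetic techniques) which may be associated with a greater risk of airway complications". The first secondary outcome in section 6.1 is "Risk of composite outcome of airway complications will be reported for each individual component of the aerosol precaution bundle".

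The adjunct-equipment list in section 9.1 ends with "aerosol boxes or drapes; as well as a free text option for other potential equipment". Boxes and drapes stand there as one item, and free text is offered in addition for equipment not already named.

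The data come from the form in Appendix 2: the anaesthetist or assistant "will be asked to complete a paper case record form (CRF; *Appendix* 2"). Its Equipment field offers a bougie, a stylet, an Oxford pillow, high-flow and low-flow nasal cannulae, "Clear plastic 'aerosol' box" and 'Other'. None of its options names a drape. Of the eleven CRF notes, none mentions one, and note 7 explains 'Other' for the airway device only.

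**The concern.** A drape is not a clear plastic box, so a respondent who used one finds no printed option that fits. That person may tick 'Other', may stretch the meaning of the box label, or may tick nothing. In the last case the record looks the same as one from a patient with no barrier.

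An item that section 9.1 names for collection is thus left to the respondent's initiative, while other items in the same list have a printed prompt. At stake is the completeness of one exposure in the component-level secondary outcome.

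Later repair is limited. Under section 9.1 any local ID is detached once the CRF is completed and is absent during the six months for which paper forms are kept. Section 9.2 says that no name, hospital number or NHS number is uploaded. After that point an unticked drape cannot readily be traced back to the notes.

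**Working it through.** **1. Text against form.** Section 9.1 names the exposure as box or drape. The CRF label names the box alone. The label is intact in the extracted text, so broken layout does not explain the difference. The mismatch is established by reading and needs no arithmetic.

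**2. The plan's own figures, for context.** Section 10.1 plans by "assuming an anticipated 5% incidence of our primary outcome in our study population, a desired error of +/-1% (absolute error") with 95% confidence. The Appendix 4 formula with N = 1,000,000, p = 0.05, d = 0.01, DEFF = 1 and Z = 1.96 gives n = Np(1−p) / [(d²/Z²)(N−1) + p(1−p)] = 1821.4, rounded up to 1822, as stated. Section 10.1 also says "with 50 centres each performing 18 procedures a day, we expect 3600 patients to be included"; over the four study days, 50 × 18 × 4 = 3600. Neither figure depends on how drapes are recorded.

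**3. How many drape users there might be.** The documents give no rate, so the following shares are assumptions. Users = share × 3600; events = users × 5%.

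| Assumed drape use | Users | Expected events at 5% |
|---|---|---|
| 0.2% | 7.2 | 0.36 |
| 1% | 36 | 1.8 |
| 3% | 108 | 5.4 |

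Over most of this range a separate drape estimate would be very imprecise even if every drape were recorded.

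**4. Effect on patients coded as unexposed.** Suppose every drape user is missed and has a risk of 10% (assumed) against 5% for everyone else. The risk among 3600 patients coded unexposed is then:
- 1% use: (3564 × 0.05 + 36 × 0.10) / 3600 = 181.8 / 3600 = 5.05%
- 3% use: (3492 × 0.05 + 108 × 0.10) / 3600 = 185.4 / 3600 = 5.15%

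The comparator hardly moves from 5.00%.

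**5. Effect on an aerosol-box odds ratio.** Take an illustrative box risk of 10% against 5%: OR = (0.10/0.90) / (0.05/0.95) = 2.11. Now place 30 missed drape users in a comparator of about 3600.
- If their risk is 10%, the comparator risk is (3570 × 0.05 + 30 × 0.10) / 3600 = 5.04% and the OR is 2.09.
- If the missed users are exactly those without a complication, the comparator risk is 178.5 / 3600 = 4.96% and the OR is 2.13.

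The shift is trivial, and its direction depends on who goes unrecorded.

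**6. Outcome-dependent reporting.** Exposure and complications are entered by the same person on the same form, so an unprompted entry could depend on the outcome. As an assumed example, let the true risk be 5%, with drapes written in for 80% of cases with a complication and 50% of those without. The apparent risk is 0.05 × 0.80 / (0.05 × 0.80 + 0.95 × 0.50) = 0.04 / 0.515 = 7.8%, and the odds are inflated 0.80/0.50 = 1.6-fold. With equal reporting in both groups there is no such bias, only fewer recorded users. The documents do not show which applies.

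**The case against.** The strongest reply is that drapes can still be captured. Section 9.1 provides free text, the CRF has 'Other', and local investigators must ensure completeness, cross-checking with the notes where appropriate. The box label may also be shorthand: section 9.1 allows an Oxford or HELP pillow while the CRF prints only the Oxford pillow, so some drape users may simply tick the box. Appendix 2 is a sample form in broken layout, the REDCap form is not shown, and the text does not settle whether the equipment 'Other' has a write-in line.

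Much of this stands, and it rules out three stronger readings that a reader might infer:
- **That drape risk cannot be reported.** Drapes written under 'Other' could be coded and reported, though probably under-counted. Only if 'Other' were a bare tick box would they be inseparable from other items, and the text does not show that.
- **That a separate drape estimate is promised.** Section 9.1 joins boxes and drapes as one item, and the Protocol never itemises the bundle. Drapes are a component by inference.
- **That missed drapes pull the aerosol-box odds ratio towards 1.** Steps 4 and 5 show a negligible effect whose direction is not fixed.

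The reply does not remove the mismatch. Free text is offered for other equipment, and drapes are already named. Shorthand helps only those respondents who read it that way. Cross-checking works only while the record can be linked and if the notes mention the drape.

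**Conclusion.** The point holds as a minor mismatch between the Protocol text and its data collection form. Section 9.1 defines a box-or-drape exposure and the CRF prompts for half of it, so the exposure is likely to be under-ascertained for the component-level secondary outcome. The extent is unknown, because neither drape use nor the completeness of 'Other' entries is given; every count in steps 3 to 6 of the working beyond the plan's own figures rests on assumed values. No particular share of lost exposures can be stated. The primary outcome, the 1822 minimum and the expected 3600 patients are untouched.

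**What to change.** Reconcile section 9.1 with the CRF and the REDCap form before data collection. Either relabel the existing box 'Aerosol box or drape', or print 'Aerosol drape' as its own tick box beside it. Report the box-or-drape exposure as section 9.1 lists it. Separate tick boxes also allow box and drape to be described individually, with the caution that drape numbers may be very small.

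The cost is one line on the paper form and one field or label in REDCap. The sample size and analysis method do not change.

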15.4	4	Appendix 4 – Sample Size Calculation 22			

2 List of Abbreviations and Definitions

AC	Airway Complication
AE	Adverse Event
AP	Aerosol Precaution
AR	Adverse Reaction
ASR	Annual Safety Report
CA	Competent Authority
CI	Chief Investigator
CRF	Case Report Form
CRO	Contract Research Organisation
DMC	Data Monitoring Committee
e-CRF	Electronic Case Report Form
EC	European Commission
GAfREC	Governance Arrangements for NHS Research Ethics Committees
ICF	Informed Consent Form
MA	Marketing Authorisation
MS	Member State
PI	Principle Investigator
Participant	An individual who takes part in a clinical trial
PPE	Personal Protective Equipment
QA	Quality Assurance
QC	Quality Control
SAD	Supraglottic airway device
SAE	Serious Adverse Event
SDV	Source Document Verification
SOP	Standard Operating Procedure
SSA	Site Specific Assessment
TMG	Trial Management Group
TSC	Trial Steering Committee

3 Summary/Synopsis

Title	Prevalence of airway complications and association with aerosol precautions – a prospective multicentre service evaluation
Protocol Short Title/Acronym	AeroComp
Protocol Version number and Date	v1.2 (13/10/2021)
Study Duration	5 days
Lead Site	Guy's and St. Thomas' NHS Foundation Trust
Chief Investigator	[name]
Medical condition or disease under investigation	Perioperative airway complications
Purpose of service evaluation	Identify current usage of aerosol precautions and incidence of airway complications in patients undergoing general anaesthesia.
Primary objective	Identify current rate of airway complications (defined as a composite of multiple individual components) in patients undergoing general anaesthesia for elective and emergency procedures.
Secondary objective(s)	 Risk of the primary outcome stratified by each individual component of the aerosol precaution bundle Individual complications that comprise the primary objective (airway trauma, aspiration, desaturation, difficult intubation, difficult ventilation, second intubator required, laryngospasm, failed intubation, emergency front-of-neck airway, oesophageal intubation). Association between risk of airway complications and patient COVID- 19 status.
Number of Subjects/Patients	~3600
Study Type	Service evaluation
Endpoints	 Primary Endpoint Composite outcome of perioperative airway complications Secondary Endpoints Individual airway complications Components of the aerosol precaution bundle

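### The COVID-19 status categories overlap in Section 9.1, differ from the CRF on symptoms, and are captured in one box that cannot be split into confirmed and suspected cases later

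*Protocol*

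**What the plan says.** COVID-19 status is described in three places in the protocol.

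- **Section 9.1 (Data to be collected).** Positive is a positive PCR or lateral flow test, "OR symptoms consistent with COVID-19 with no SARS-CoV-2 test available; OR recent exposure to SARS-CoV-2". The second group reads "Negative: RT-PCR or lateral flow test negative for SARS-CoV-2 infection; AND actively cohorted with other COVID-19 negative patients", and also requires self-isolation. Unclear is no test result in a patient without risk factors, "OR not self-isolated according to institutional guidelines; OR not in a COVID-19-free pathway".
- **Appendix 2 (CRF).** The table is partly broken in the text available, but the Positive line is legible: a positive test, then COVID-19 "symptoms; recent exposure". CRF notes 1 to 11 give no rule for this item.
- **Section 6.1 (secondary outcomes).** The composite is to be related to "confirmed/suspected COVID-19 infection, known negative COVID-19 infection without any potential COVID-19 risks, and all other patients".

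Section 9.1 says that "the anaesthetist or anaesthetic assistant (e.g. operating department practitioner, anaesthetic nurse) will be asked to complete a paper case record form". It also says that any local ID is detached once the form is complete and is not uploaded. The association with COVID-19 status is a secondary objective in the Synopsis.

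**The concern.** A categorical exposure needs groups that exclude one another and mean the same thing wherever they are written. Here the conditions are joined by OR across groups, with no order of precedence in Section 9.1 or on the form. The form and Section 9.1 also differ on what symptoms count for. The person completing the CRF may therefore face two valid boxes, and two people could tick different ones for the same patient.

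What is at stake is the secondary association between COVID-19 status and airway complications. The Introduction says that infection itself may raise airway risk and that positive or unknown status calls for more PPE. Status could therefore also be used as an adjustment variable for the aerosol-precaution associations. A statistical analysis plan could not repair the problem, because test result, symptoms and exposure are merged into one item when recorded, and no other listed item holds them.

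**Working it through.** **1. Plan's own figure.** The protocol attaches no number to this item. Its sample size (Section 10.1, Appendix 4) uses N = 1,000,000, p = 0.05, d = 0.01, design effect 1 and Z = 1.96:

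n = Np(1−p) / [(d²/Z²)(N−1) + p(1−p)] = 47,500 / (26.031 + 0.0475) = 1821.4, rounded up to 1822.

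This reproduces the stated figure. COVID-19 status does not enter it.

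**2. Overlap under Section 9.1.** Cross five features: test (positive, negative, none), symptoms, recent exposure, cohorted in a COVID-free pathway, and self-isolated (each yes or no). This gives 3 × 2 × 2 × 2 × 2 = 48 profiles. In the Unclear definition, no risk factors is read as no symptoms and no exposure.

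| Test | Positive + Unclear | Positive + Negative | Positive only | Unclear only | Negative only |
|---|---|---|---|---|---|
| Positive (16) | 12 | 0 | 4 | 0 | 0 |
| Negative (16) | 6 | 2 | 0 | 6 | 2 |
| None (16) | 9 | 0 | 3 | 4 | 0 |
| All (48) | 27 | 2 | 7 | 10 | 2 |

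So 27 + 2 = 29 of 48 profiles meet two categories. All 8 test-negative exposed profiles meet Positive: 2 of them also meet Negative and 6 also meet Unclear. These are counts of profiles, not of patients; the protocol does not say how common each one is.

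**3. Section 9.1 against the CRF.** Section 9.1 counts symptoms only when no test is available; the CRF has no such limit. The two wordings differ for test-negative, symptomatic, unexposed patients, which is 2 × 2 = 4 profiles (cohorted yes/no, isolated yes/no). Under Section 9.1, one of these is Negative and three are Unclear. On the form, all four also meet Positive. This comparison does not rely on the broken Unclear line of the CRF.

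**4. Section 6.1.** Its third group is a remainder, so a PCR-positive patient outside a COVID-free pathway goes to the first group. Its second group excludes anyone with a potential risk, so an exposed test-negative patient cannot be there. Read with Section 9.1, this implies an order: confirmed or suspected, then negative without risk, then all others. Neither the CRF nor its notes state that order.

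**5. Possible effect on the odds ratio (illustration only).** Assume the risk acts through infection itself, is 5% in uninfected patients (the protocol's overall anticipated incidence, borrowed here), and has a true odds ratio of 2. The risk in infected patients is then (2 × 0.05/0.95) / (1 + 2 × 0.05/0.95) = 9.52%. If a share s of the Positive group is infected, the group's risk is s × 9.52% + (1 − s) × 5%:

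| Assumed s | Risk in Positive group | Observed odds ratio against 5% |
|---|---|---|
| 75% | 8.39% | 1.74 |
| 50% | 7.26% | 1.49 |
| 25% | 6.13% | 1.24 |

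Neither s nor the odds ratio of 2 is in the protocol.

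**The case against.** The best defence is that Section 6.1 already orders the groups. Its residual third group settles the 27 Positive-and-Unclear profiles, and its exclusion of any potential risk settles the 2 Positive-and-Negative ones. On this view, symptoms without a test, or exposure, simply spell out what suspected means, so Section 6.1 does not contradict Section 9.1 on the first group. This stands as a reading of the intended analysis. It does not help at data capture, because the person ticking one box does not see that order. Nor does it remove the difference between Section 9.1 and the CRF on symptoms. Local cross-checking against notes reduces recording errors but supplies no rule.

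A reader might infer that the COVID-19 association is diluted. The documents do not support that as a fact. The stated outcome concerns confirmed or suspected infection, so including suspected patients is misclassification only if the target is proven infection. If risk acts through the precautions, which also apply to patients of unknown status, attenuation could be small or absent. With three groups, and errors that may vary with the person recording both status and complications, the direction is not guaranteed.

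A reader might also infer residual confounding in the PPE odds ratios. That depends on status entering the multivariable model, and Section 10.2 does not name its covariates.

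**Conclusion.** The point holds as a fault of definition and data capture. The Section 9.1 categories are not mutually exclusive as worded (29 of 48 profiles meet two), and the CRF departs from Section 9.1 for 4 profiles. The order implied by Section 6.1 is missing from the form, and the single box does not allow confirmed and suspected cases to be separated afterwards. Classification for the secondary COVID-19 association can therefore be inconsistent between people completing the form.

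The profile counts rest on a literal reading of the wording. The size and direction of any bias cannot be computed from the protocol; the odds ratios of 1.74, 1.49 and 1.24 only show what attenuation would look like under the stated assumptions. The primary incidence and the sample size of 1822 are unaffected. The change is worth making because the lost detail cannot be recovered later, but the point does not undermine the main aim.

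**What to change.** - Use one identical, mutually exclusive definition in Section 6.1, Section 9.1 and the CRF, and print the order of precedence on the CRF. State explicitly where test-negative patients with symptoms, and test-negative patients with a recent exposure, belong.
- Replace the single box on the CRF and e-CRF with separate ticks: test result (positive, negative, none), symptoms, recent exposure, and isolated/cohorted. Derive the Section 6.1 groups from these by the stated order, so that the grouping no longer depends on the person completing the form.
- Report test-positive patients separately from suspected ones, as a descriptive or sensitivity analysis.

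The cost is a few extra tick boxes and a short derivation rule. The confirmed group may be small, so its separate estimate may be imprecise.
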